**Scope:**

This document covers (a) Phase 1 PROVIDENT model development, (b) the Phase 2 randomized cluster trial (39 Rhode Island municipalities randomized 1:1 to PROVIDENT vs comparator), (c) a parallel Phase 2 implementation study (surveys/focus groups; staff enrollment; no randomization of individuals), and (d) the COVID-19 supplement study. The ClinicalTrials.gov record (NCT05096429) reports only the Phase 2 randomized cluster trial. The implementation study, Phase 1 model development, and COVID supplement are not included.

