## **Study Sample**

This trial will not enroll individual participants. Randomization and assessment of study outcomes will occur at the municipal level, and all study outcomes will be assessed at this same level. However, during the study period, all persons who reside in Rhode Island or who experience a qualifying event—defined as a fatal or non-fatal overdose captured by the state’s multicomponent overdose surveillance system—may contribute data to either the PROVIDENT model or the study outcomes.

Based on 2016 data, we expect to observe approximately 1,800 events of fatal or non-fatal overdoses per year (see Table S1 below), which will be analyzed to evaluate the effects of the community-level intervention. Since all 39 cities/towns in Rhode Island will participate in the intervention trial, and due to the population-based nature of the fatal and non-fatal overdose surveillance system, every Rhode Island city and town may be eligible for inclusion in this study.

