## **Power Calculation and Sample Size**

To ensure adequate power, we will consider as the primary endpoint both fatal and non-fatal overdoses occurring at the municipal level. These events will be defined as described in the Primary and Secondary

Outcomes Measures above. These data are captured in the Rhode Island Office of the State Medical Examiner's drug overdose death records database and the Rhode Island Emergency Medical Services Information System. To estimate the power to detect significant differences between overdose rates in treatment and control cities/towns, we examined 2016 municipal-level overdose data. We used a stratified randomization scheme to conduct power simulations. Power was calculated for relative reductions in combined fatal/nonfatal overdose rates ranging from 15 to 30 percent. We used data from 2016 to set the underlying statewide overdose rate. We simulated randomization of each city to treatment versus control, estimated the expected number of events for each city based on population size and treatment assignment, and then used standard calculations for two-sample comparisons of Poisson rates. Due to the finite sample of municipalities with widely varying population sizes, the person-time of exposure in the control and treatment groups will vary depending on how cities are randomized. We therefore calculated power for several simulated randomizations, with 10 randomly selected instances shown (Figure S1). As shown, we will have at least 95% power to detect a >25% reduction in the treatment arm compared to cities/towns assigned to the control arm. These estimates are conservative: we assumed only one year of post-intervention follow-up time, whereas we anticipate two years based on the project timeline.

**Figure S1:** Power curves for the PROVIDENT trial from simulated randomizations (ten randomly selected instances are shown).

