## **B. Analysis and Data Management**

### **Analysis:**

The analysis plan will be finalized and uploaded to the Open Science Framework (osf.io) before the start of the data analysis in accordance with the pre-specified analysis plan. We will employ standard methods for community intervention trials. The intervention effect will be quantified as a composite fatal and non-fatal overdose incidence rate ratio. We will have at least 5 years of data (from 2016 to 2020) to serve as the pre-intervention period. The trial formally began in November, 2021. We will exclude a six-month 'ramp up' period in all analyses to allow time for the targeted interventions to be deployed. We will have approximately two years of post-intervention data from May 15, 2022, to August 15, 2024.

We will use generalized linear mixed-effect modeling with Poisson or negative binomial link functions to estimate incidence rate ratios comparing overdose rates in treatment cities/towns to control cities/towns. Each municipality will have its own random intercept and slope to account for pre-intervention differences and time trends. Municipal population size will be incorporated as an offset, and 95% confidence intervals will be calculated using standard bootstrapping techniques to account for possible overdispersion of the data and the relatively small number of geographic units per arm. Although we will use stratified randomization to reduce pre-intervention differences in the treatment and control groups, potential biases from the imbalance can be corrected by including other covariates in the model. For example, measures of municipal-level racial/ethnic composition (e.g., percentage Hispanic/ Latino) will be included as covariates, given some evidence of imbalance in these variables between the two arms. Next, we will construct time-lagged regression models to consider the delayed impact of the interventions by staggering outcomes by zero to 6 months.

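### An unspecified standard bootstrap is the SAP's only stated correction for few towns per arm, and plausible versions of it run above 5% type I error with 39 very unequal towns

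*SAP*

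**What the plan says.** The SAP (B, Analysis) sets the primary model: "We will use generalized linear mixed-effect modeling with Poisson or negative binomial link functions to estimate incidence rate ratios". Each municipality has its own random intercept and slope, and population enters as an offset. For inference, 95% "confidence intervals will be calculated using standard bootstrapping techniques to account for possible overdispersion of the data and the relatively small number" of units per arm.

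The resampling unit, the kind of bootstrap (nonparametric or model-based), the interval type and the number of replicates are not given. Neither document names another small-sample correction, a randomisation-based test or an alpha level. The protocol's analysis text (section 7, Phase 2 Cluster randomized trial) mentions Poisson regression and GEE but gives no interval method.

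The design has "39 Rhode Island municipalities randomized 1:1 to PROVIDENT vs comparator", with stratified randomisation. The power section recognises the inequality of the units: "Due to the finite sample of municipalities with widely varying population sizes". The SAP also says that the analysis plan will be finalised and posted publicly before analysis, and it plans a sensitivity analysis without Providence and a comparable town in the other arm.

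**The concern.** The bootstrap is justified as the number of independent units grows. It can address overdispersion if the right unit is resampled, but it does not repair a shortage of units; it shares that weakness. A nonparametric bootstrap of n units reproduces a variance too small by the factor (n-1)/n, and percentile limits make no allowance for estimating that variance from few units. When a handful of units carry most of the information, the effective n is well below the nominal one.

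This interval is the trial's main answer. If it is too narrow, ordinary differences between towns in how overdoses changed over time can pass for an intervention effect. Because the method is open, bootstraps of materially different width would all fit the text.

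**Working it through.** **Inputs from the documents.** 39 towns in four strata, counted from Table S1: Urban-High 6, Urban-Low 4, Non-Urban-High 15, Non-Urban-Low 14. Populations run from 1,051 to 178,042. There are 5 years pre-intervention (2016-2020) and 2.25 years post (15 May 2022 to 15 August 2024). The Table S1 rows add to 1,416 non-fatal + 323 fatal = 1,739 events; the printed totals give 1,461 + 336 = 1,797. The difference does not affect what follows. A two-sided 5% level is assumed from the 95% interval.

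**The plan's own figure.** The only related design figure is at least 95% power for a >25% reduction, from a two-sample Poisson comparison over one year. With 1,797 events and equal exposure, the expected counts are 898.5 (control) and 0.75 × 898.5 = 673.9 (treated). The SE of the log rate ratio is √(1/673.9 + 1/898.5) = 0.0510, and |ln 0.75|/0.0510 = 0.2877/0.0510 = 5.65. Power is Φ(5.65 - 1.96) > 99.9%. Over 5,000 stratified randomisations the minimum was 99.91%. The statement therefore holds as a lower bound. It contains no between-town variance and says nothing about interval coverage.

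**How unequal the units are.**
- Providence: 541/1,739 = 31% of events. The five largest contributors: (541 + 158 + 157 + 157 + 69)/1,739 = 1,082/1,739 = 62%.
- Effective number of equal towns by events: (Σe)²/Σe² = 1,739²/395,853 = 7.6.
- Chance that a resample of whole towns omits Providence: (38/39)^39 = 0.363. Within an arm of 20 it is (19/20)^20 = 0.358.
- Resampling within arm and stratum, with even splits assumed, leaves 3 towns per Urban-High cell and 2 per Urban-Low cell. The factor (n-1)/n is then 2/3 and 1/2, against 19/20 for a whole arm of 20. Urban-High alone has (541 + 158 + 157 + 157 + 69 + 68)/1,739 = 1,150/1,739 = 66% of events.

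**Simulation under no effect.** Table S1 populations and lightly smoothed town rates were used, with stratified allocation. Town i's log rate changes by u_i ~ N(0, SD²). The SD is not in the documents; 0 to 0.5 was assumed. There were two approximations to the planned model: (a) a normal approximation to the random-slope model (2,500 trials, 400 resamples); (b) a binomial mixed model conditional on each town's total, logit p_i = ln(2.25/5) + b0 + b1·arm_i + u_i (1,000 trials, 200 resamples). Intervals were percentile 95%. Monte Carlo SE is about 0.5 points for (a) and 0.8 for (b).

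Type I error in %, shown as (a)/(b) where both were run:

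| Method | SD 0 | 0.1 | 0.2 | 0.3 | 0.5 |
|---|---|---|---|---|---|
| Towns resampled within arm | 7.0/6.8 | 6.7/7.9 | 7.0/7.6 | 8.4/8.5 | 7.1/6.6 |
| Towns within arm × stratum | 12.7/11.4 | 12.3/12.0 | 11.3/11.0 | 11.8/12.2 | 10.8/9.6 |
| Parametric | 4.6/4.0 | 9.2/10.4 | 7.7/7.9 | 8.7/8.1 | 8.0/7.4 |
| Town-month rows, simple Poisson estimator | 0.3 | 8.3 | 33.5 | 50.0 | 64.9 |
| Stratified re-randomisation test (a) | 5.4 | 4.6 | 5.1 | 6.5 | 5.4 |
| REML with t on 37 df (a) | 3.6 | 6.8 | 5.8 | 6.4 | 5.6 |

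The row bootstrap is conservative at SD 0 because it counts stable rate differences between towns as noise. It fails as SD grows because it ignores that a town's months move together. A separately coded null simulation with a random-effects estimator gave 6-8% within arm, 11-14% within arm × stratum and 4-6% for re-randomisation, in line with the table.

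**The case against.** The best defence is that the excess rests on two things the documents do not give: the kind of bootstrap and the town-level SD. With no variation between towns in their change over time, the parametric version gave 4.0-4.6% and the row version 0.3%. A reader might infer that the planned interval is bound to exceed 5%. The documents do not support that, and this part of the objection stands.

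A reader might also infer error rates of tens of percent. Among the versions tested here those arise when rows are resampled and clustering is ignored. Estimators that weight towns by events with fixed town effects also give larger figures, but they are not the mixed model that the SAP plans. For the closest simple match, towns resampled within arm, the excess is modest. The simulation uses pre/post totals without covariates and does not replicate the full time-trend model.

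SD 0 is nevertheless an unlikely state by the SAP's own account. It anticipates overdispersion, gives each town its own slope, and describes a June 2023 protocol change that sent overdose-related 911 calls in Providence to EMS, the source of the non-fatal outcome. That is a town-specific shift inside the post-intervention period. The sensitivity analysis without Providence is sensible but leaves the primary interval as it is. The promised final plan could settle the method, so it is the place to make the correction; it is not evidence that the choice has been made.

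**Conclusion.** The concern holds in a limited form. The plan relies on an unspecified bootstrap for a protection that the bootstrap does not supply with 39 very unequal towns. For an assumed SD of 0.1 to 0.5, every bootstrap tested exceeded 5%. Versions close to the planned model gave about 7-8.5% (towns within arm), 7-10% (parametric) and 10-12% (towns within arm and stratum, which reached 12.7% at SD 0). That is roughly 1.4 to 2.4 times nominal. Row resampling could be far worse.

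The direction is well supported. The size depends on the bootstrap chosen and on an SD that the documents do not report. This should be fixed before the analysis plan is finalised, with medium confidence in the magnitude. It does not call the design or the point estimate into question.

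**What to change.** Keep the mixed-model incidence rate ratio as the estimate. For the primary p-value and 95% interval, specify one of the following before the analysis:

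- A test that re-draws the actual stratified 1:1 allocation of the 39 towns, with the interval by test inversion. Simulated error was 4.6-6.5%, mean 5.4%. The SAP must state the allocation algorithm, because the test has to re-draw it. If strata are split as evenly as possible (assumed), there are 20 × 6 × (2 × 6,435) × 3,432 ≈ 5.3 billion allocations, so p-values are not coarse.
- A small-sample cluster-level interval, for example REML with t on 37 df (39 towns less 2 arms). Simulated error was 3.6-6.8%. The evidence does not clearly favour either option.

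If a bootstrap is retained, state that whole municipalities are resampled, give the interval type and number of replicates, and label it supportive. State alpha and sidedness.

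The cost is SAP wording, computing time and a somewhat wider interval. No new data are needed.

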## Expected enrollment distribution for cities/towns in Rhode Island (Table S1)

**Table S1:** The target population for this grant will be secondary data events from overdose surveillance records in the State of Rhode Island, randomized at the level of the city/town (2016).

City/Town	Population	Non-Fatal ODs	All fatal ODs	Annual OD Rate (per 100,000)	Urbanicity	Strata
Barrington	16310	9	1	61.31	Non-Urban	Non-Urban-Low
Bristol	22954	15	3	78.42	Non-Urban	Non-Urban-Low
Burrillville	15955	6	1	43.87	Non-Urban	Non-Urban-Low
Central Falls	19376	26	5	159.99	Urban	Urban-Low
Charlestown	7827	12	2	178.87	Non-Urban	Non-Urban-High
Coventry	35014	35	6	117.10	Non-Urban	Non-Urban-High
Cranston	80387	141	16	195.31	Urban	Urban-High
Cumberland	33506	8	10	53.72	Non-Urban	Non-Urban-Low
East Greenwich	13146	7	1	60.86	Non-Urban	Non-Urban-Low
East Providence	47037	51	8	125.43	Urban	Urban-Low
Exeter	6425	7	0	108.95	Non-Urban	Non-Urban-High
Foster	4606	2	1	65.13	Non-Urban	Non-Urban-Low
Glocester	9746	0	2	20.52	Non-Urban	Non-Urban-Low
Hopkinton	8188	17	2	232.05	Non-Urban	Non-Urban-High
Jamestown	5405	1	0	18.50	Non-Urban	Non-Urban-Low
Johnston	28769	42	14	194.65	Non-Urban	Non-Urban-High
Lincoln	21105	17	1	85.29	Non-Urban	Non-Urban-High
Little Compton	3492	1	1	57.27	Non-Urban	Non-Urban-Low
Middletown	16150	10	3	80.50	Non-Urban	Non-Urban-High
Narragansett	15868	11	3	88.23	Non-Urban	Non-Urban-High
New Shoreham	1051	0	2	190.30	Non-Urban	Non-Urban-High
Newport	24672	29	3	129.70	Urban	Urban-Low
North Kingstown	26486	15	7	83.06	Non-Urban	Non-Urban-High
North Providence	32078	39	13	162.10	Urban	Urban-Low
North Smithfield	11967	2	1	25.07	Non-Urban	Non-Urban-Low
Pawtucket	71148	129	29	222.07	Urban	Urban-High
Portsmouth	17389	12	7	109.26	Non-Urban	Non-Urban-High
Providence	178042	449	92	303.86	Urban	Urban-High
Richmond	7708	4	2	77.84	Non-Urban	Non-Urban-Low
Scituate	10329	4	5	87.13	Non-Urban	Non-Urban-High
Smithfield	21430	3	4	32.66	Non-Urban	Non-Urban-Low
South Kingstown	30639	17	2	62.01	Non-Urban	Non-Urban-Low
Tiverton	15780	3	2	31.69	Non-Urban	Non-Urban-Low
Warren	10611	13	2	141.36	Non-Urban	Non-Urban-High
Warwick	82672	132	25	189.91	Urban	Urban-High
West Greenwich	6135	4	1	81.50	Non-Urban	Non-Urban-High
West Warwick	29191	57	11	232.95	Urban	Urban-High
Westerly	22787	46	6	228.20	Non-Urban	Non-Urban-High
Woonsocket	41186	40	29	167.53	Urban	Urban-High
Total	1052567	1,461	336			

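### The primary analysis names no role for the four randomisation strata, leaves the treatment contrast unwritten and picks covariates on imbalance; intervals will be too wide if overdose trends differ between strata

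*SAP*

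**What the plan says.** The Protocol (Scope) describes "39 Rhode Island municipalities randomized 1:1 to PROVIDENT vs comparator". The SAP says, under Power Calculation and Sample Size, "We used a stratified randomization scheme to conduct power simulations", and under Analysis, "Although we will use stratified randomization to reduce pre-intervention differences in the treatment and control groups", with other covariates available to correct what imbalance remains. The text does not name the stratification factors. They are inferred here from the Strata column of Table S1, which carries four labels of the type "Non-Urban-High".

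On the model, the SAP states: "We will use generalized linear mixed-effect modeling with Poisson or negative binomial link functions to estimate incidence rate ratios". It adds: "Each municipality will have its own random intercept and slope to account for pre-intervention differences and time trends". Population is an offset, and 95% intervals come from a standard bootstrap. On baseline data: "We will have at least 5 years of data (from 2016 to 2020) to serve as the pre-intervention period". The post-intervention window runs from 15 May 2022 to 15 August 2024.

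On covariates, racial/ethnic composition is offered as an example; such measures "will be included as covariates, given some evidence of imbalance in these variables between the two arms". Strata are named neither as a model term nor as bootstrap blocks, and no equation shows which coefficient is the treatment effect. The same section says the analysis plan is still to be finalised and posted before data analysis starts.

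**The concern.** An analysis should normally respect the groups within which units were randomised. Stratification makes the arms alike on the stratum factors, so the estimate varies less from one allocation to another. An analysis that ignores the strata counts differences between them as chance variation between towns. The estimate keeps its precision but the reported interval is too wide, and power is lost.

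The covariate rule is a separate weakness. Imbalance after allocation says nothing about whether a variable predicts overdose rates, and an open list settled after the allocation is known gives the analyst room for choice in a 39-unit analysis. The SAP has a strong candidate for adjustment in its own strata, yet names a variable for which it gives only evidence of imbalance.

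**Working it through.** **Inputs from Table S1.** Counts and pooled 2016 rates per 100,000, from the rows:

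| Stratum | Towns | Events | Population | Rate |
|---|---|---|---|---|
| Non-Urban-Low | 14 | 109 | 212,644 | 51.3 |
| Non-Urban-High | 15 | 306 | 234,134 | 130.7 |
| Urban-Low | 4 | 174 | 123,163 | 141.3 |
| Urban-High | 6 | 1,150 | 482,626 | 238.3 |

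The rows sum to 1,739 events; the printed totals give 1,461 + 336 = 1,797. Row sums are used, and the difference does not affect the result.

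**The plan's own figure.** The SAP claims at least 95% power for a reduction above 25%, from a two-sample Poisson comparison with one statewide rate and one year. With an even split of 1,739 events, control expects 869.5 and treatment 0.75 × 869.5 = 652.1. SE of the log ratio = √(1/869.5 + 1/652.1) = 0.0518; |ln 0.75|/0.0518 − 1.96 = 5.55 − 1.96 = 3.59, so power is 99.98%. Over 5,000 simulated stratified allocations it was at least 99.9% (two-sided alpha 0.05 assumed). The claim holds as a lower bound. The calculation has no stratum-specific rates and no town-level variation, so it says nothing on whether the analysis needs the strata.

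**Strata in the described model, when strata share a trend.** A Poisson mixed model with town random intercept and slope, 5 pre-years, 2.25 post-years, effect = arm × post and true ratio 0.75 was fitted to 200 simulated trials per setting. Mean SE of the log rate ratio:

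| Random-slope SD per year (assumed) | No strata | + stratum | + stratum and stratum × post |
|---|---|---|---|
| 0 | 0.0428 | 0.0428 | 0.0434 |
| 0.05 | 0.0716 | 0.0716 | 0.0720 |
| 0.10 | 0.0809 | 0.0810 | 0.0823 |

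A stratum main effect changes nothing. The interaction costs at most 0.0823/0.0809 − 1 = 1.7% in SE when it is not needed.

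**Strata that differ in change.** For town *i*, let *d*ᵢ = ln(post events/2.25) − ln(pre events/5), with variance 1/pre + 1/post + τ², where τ is the SD of town-level change. Each town is its own baseline, and *d* is regressed on arm with and without stratum. A stratum term here is the stratum × post term of the full model. With τ = 0.20 and true ratio 0.75:

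| SD of change between strata (assumed) | SE without | SE with | Fall in SE |
|---|---|---|---|
| 0 | 0.089 | 0.089 | 0% |
| 0.10 | 0.094 | 0.088 | 6% |
| 0.20 | 0.106 | 0.089 | 16% |
| 0.30 | 0.125 | 0.089 | 29% |

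The 16% is (0.106 − 0.089)/0.106. In that row power goes from about 77% to 87%. Without the term, coverage of the nominal 95% interval is about 97.5%, while the actual spread of the estimate barely moves: the interval is too wide, not the estimate noisier. With the term, coverage was 92–94% using normal critical values, so part of the power gain would go to a small-sample correction.

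**If the contrast were post-period only, without baseline.** A negative binomial model on post-period counts gave mean SE 0.192 without strata and 0.124 with (power 22% and 64%), with no town-level change. The estimate's actual SD was 0.125 and 0.131, and coverage without strata was 99.7%. Once each town's pre-period rate was added, strata made no difference (0.0574 and 0.0584).

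**The case against.** The strongest reply is that each town's intercept and slope adjust for baseline more finely than a four-level stratum can. That stands for baseline level: the stratum main effect gains nothing. A reader might infer a much larger loss from Table S1, where the strata explain 71% of the variance in 2016 log rates and the SD falls from 0.713 to 0.400, which suggests a standard error up to 1 − 0.400/0.713 = 44% smaller. The documents do not support that. The figures describe rate levels in one year, the low/high labels appear to be built from those same rates, and the town intercepts with five pre-years already absorb level.

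It is also fair that Table S1 covers a single year, so the documents do not show how far strata differ in change. That is why the result is given as a range starting at zero. Such differences are still plausible. The comparison spans COVID-19, and Aim 2 of the Protocol's COVID-19 supplement asks whether the pandemic's relation to overdose is stronger in some types of community.

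The SAP reports bootstrap intervals rather than model-based standard errors. The bootstrap was not simulated here. The same reasoning applies, because resampling towns without regard to stratum puts between-stratum differences in change into the interval.

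Finally, strata are unnamed rather than excluded, and the plan is not final. Nor do the documents show that racial/ethnic composition lacks prognostic value, so moving it out of the primary model would be a preference. Both points stand.

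**Conclusion.** The point holds as a gap in specification with a conditional cost. The SAP stratifies the randomisation but gives the strata no stated role in the model or bootstrap, does not write the treatment contrast, and justifies covariates by observed imbalance from an open list.

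On an arm-by-post-period reading, leaving out stratum-by-period costs nothing if strata share a trend. It makes the standard error too large if they do not: including the term lowers it by about 16% when stratum and town changes each have SD 0.20, and by 6% to 29% as the stratum SD runs from 0.10 to 0.30. An SD of 0.20 on the log scale means changes differing by a factor of about e^0.20 = 1.22. The consequence is conservative intervals and lost power, not bias. The loss is larger on a post-period-only contrast without baseline, which the SAP's wording does not suggest but does not rule out.

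This rests on assumed SDs of change, two-sided alpha 0.05, town rates near their 2016 values, strata read from Table S1, and a change-score approximation to the full mixed model.

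**What to change.** Before outcome data are analysed, amend the Analysis section to:

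- write the model out and define the treatment effect as the arm-by-post-period term;
- add stratum and stratum-by-post-period as fixed effects;
- resample whole towns within stratum and arm in the bootstrap;
- close the covariate list, with each entry justified on prognostic grounds. Racial/ethnic composition may stay if justified that way.

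The cost is SAP wording and 3 + 3 = 6 fixed effects. For the town-level comparison of change, degrees of freedom go from 39 − 2 = 37 to 39 − 5 = 34. The cost in standard error is close to nil when strata do not differ.

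A small-sample correction is still needed and should be named. Under an even split, Urban-Low has two towns per arm and Urban-High three. A plain bootstrap of a mean of *n* units understates its variance by (*n* − 1)/*n*, which is 1/2 and 2/3 in those cells, so stratified resampling without a correction would risk replacing intervals that are too wide with ones that are too narrow.
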